Following an ad-hoc interim assessment of the PK data by the IMC and SOC, adolescents and children 8 years and above will receive higher starting doses as outlined in [Table 2](#). Subjects already enrolled should receive the adjusted doses (4 or 10 mg eq) as soon as practicable, per his or her randomized assignment.

Subjects enrolled in accordance with earlier protocol versions will continue with his or her assigned dose until Week 24. All newly enrolled subjects (in accordance to Version 6) will be given either 10 mg eq or placebo.

In the OLE phase, subjects will receive 10 mg *eq*/day of balovaptan (see [Table 2](#) for further details). Details of tablet administration will be provided in the Instructions for Use.

Guidelines for treatment interruption or discontinuation are provided in Section [5.2](#).

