5.3.5.4 Abnormal Laboratory Values

Not every laboratory abnormality qualifies as an adverse event. A laboratory test result should be reported as an adverse event if it meets any of the following criteria:

- Accompanied by clinical symptoms
- Results in a change in study treatment (e.g., dosage modification, treatment interruption, or treatment discontinuation)

- Results in a medical intervention (e.g., potassium supplementation for hypokalemia) or a change in concomitant therapy
- Clinically significant in the Investigator's judgment

It is the Investigator's responsibility to review all laboratory findings. Medical and scientific judgment should be exercised in deciding whether an isolated laboratory abnormality should be classified as an adverse event.

If a clinically significant laboratory abnormality is a sign of a disease or syndrome (e.g., alkaline phosphatase and bilirubin 5 times the upper limit of normal (ULN) associated with cholecystitis), only the diagnosis (i.e., cholecystitis) should be recorded on the Adverse Event eCRF.

If a clinically significant laboratory abnormality is not a sign of a disease or syndrome, the abnormality itself should be recorded on the Adverse Event eCRF, along with a descriptor indicating if the test result is above or below the normal range (e.g., "elevated potassium", as opposed to "abnormal potassium"). If the laboratory abnormality can be characterized by a precise clinical term per standard definitions, the clinical term should be recorded as the adverse event. For example, an elevated serum potassium level of 7.0 mEq/L should be recorded as "hyperkalemia".

Observations of the same clinically significant laboratory abnormality from visit to visit should not be repeatedly recorded on the Adverse Event eCRF, unless the etiology changes. The initial severity of the event should be recorded, and the severity or seriousness should be updated any time the event worsens.

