6.3 ANALYSIS POPULATIONS

6.3.1 Safety Analysis Population

All subjects who have received at least one dose of the study medication, whether prematurely withdrawn from the study or not, will be included in the safety analysis population. Data will be analyzed according to the treatment as randomized. Any dosing error will be reviewed and the implications of such errors on safety interpretation will be assessed.

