6.3.3 Efficacy Analysis Population

6.3.3.1 *For All Subjects Enrolled prior to Version 6 of the Protocol:* **Modified Intent-To-Treat Population**

The modified intent-to-treat (mITT) population is defined as consisting of all subjects who give informed consent, are randomized, received at least one dose of double-blind medication, and for whom a baseline and at least one post-dose assessment is available. Subjects in first adolescent/first children cohorts with dose adjustments, or who were on a different dose than the final dose for their age group, will be excluded from the primary efficacy analysis, and will not contribute to the approximately 160 evaluable subjects expected in the mITT population (see Section 4.2.1). Data will be analyzed according to the treatment as randomized.

The mITT population is the primary population of interest.

Per-Protocol Population

The Per-Protocol (PP) population will be precisely defined in the statistical analysis plan, which will be finalized before database closure, as the subset of the mITT population without major protocol deviations.

The PP population will not be analyzed if this population comprises more than 90% or less than 50% of the mITT population. Only the key efficacy outcome measures (see Section 3.4.1) will be analyzed using the PP population.

6.3.3.2 *For Subjects Enrolled in Accordance to Version 6 of the Protocol:*

Intent-To-Treat Population

The intent-to-treat (ITT) population is defined as consisting of all subjects who give informed consent, are randomized, and receive at least one dose of double-blind medication. Subjects with dose adjustments or interruptions, or who were on a different dose than the final dose for their age group, will be excluded from the primary efficacy analysis and will not contribute to the approximately 160 evaluable subjects expected after 24 weeks. Data will be analyzed according to the treatment as randomized.

The ITT population is the primary and the population assessed for efficacy.

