#### **4.2.1         Safety Population**

- Safety Global

The “Safety Global” population consists of all subjects who gave informed consent and received at least one dose of study medication, whether prematurely withdrawn from the study or not.

Data will be summarized according to treatment classified as derived from PK exposure: Placebo, Low Tertile, Medium Tertile, High Tertile and All Treated with Active.

- Safety Inferential

The “Safety Inferential” population consists of the subset of the “Safety Global” population that is identified to address the primary efficacy study objective.

Data will be summarized according to treatment classified as: Placebo, 10mg equivalent.

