#### **4.2.2         Efficacy Population**

- Efficacy ITT Global

The “Efficacy Global” population consists of all subjects who gave informed consent and received at least one dose of study medication, whether prematurely withdrawn from the study or not.

Data will be summarized according to treatment classified as derived from PK exposure: Placebo, Low Tertile, Medium Tertile, High Tertile.

- Efficacy ITT Inferential

The “Efficacy ITT Inferential” population is the primary population of interest. It consists of the subset of the “Efficacy Global” population obtained by pooling data from subjects taking balovaptan 10 mg equivalent or the concurrently randomized placebo in the corresponding age band and in the same randomization stage, as highlighted in orange in Table 3, and belonging to patterns c) or d), as highlighted in yellow in Table 4. Subjects with dose adjustments or interruptions, or on a different dose than the final dose for their age group, are excluded and do not contribute to this analysis population.

Data will be summarized according to treatment classified as: Placebo, 10mg equivalent.

The following Table shows the combination of subjects' patterns (described in Table 4) to identify the Safety and Efficacy analyses population/dataset:

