**Table 5. Patterns of subjects' disposition identifying Safety and Efficacy Analysis Population/Dataset**

| Analysis Population:            | Analysis dataset:             |                                   |
|---------------------------------|-------------------------------|-----------------------------------|
|                                 | First Part (8 weeks)          | Main Part (24 weeks)              |
| Safety Global            | a + 1 st part of b | 2 nd part of b + c + d |
| Safety Inferential       | -                             | c + d                             |
| Efficacy ITT Global      | -                             | 2 nd part of b + c + d |
| Efficacy ITT Inferential | -                             | c + d                             |

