#### **4.5.2 Interim Analysis**

The populations assessed at the Interim Analysis will be the “Safety Inferential” and the “Efficacy ITT Inferential” with all subjects randomized prior to 21FEB2019, which is the date of the last subject expected to provide 12 week data for the 10mg-Placebo comparison by 16MAY19.

The efficacy interim analysis will focus on the outcome measures derived from Vineland™-II and, only descriptively, from PedsQL v4.0 Generic Core Scale, CGI-I and CGI-S.

Summary statistics will be provided for the overall population and for the adolescents/ children subgroups separately.

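### The only 10 mg equivalent versus placebo safety summary in the SAP inherits the efficacy set's exclusion of subjects with dose interruptions, so an adverse event that causes a dose hold can remove its own subject from the table

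*SAP*

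**What the plan says.** SAP 4.2.1 sets up two safety populations. Safety Global holds every dosed subject and is tabulated as placebo, three tertiles of PK exposure, and all active subjects together. Safety Inferential is the part of that "population that is identified to address the primary efficacy study objective", tabulated as placebo and 10 mg equivalent.

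The set for that objective is Efficacy ITT Inferential in SAP 4.2.2, where "Subjects with dose adjustments or interruptions, or on a different dose than the final dose for their age group, are excluded". SAP Table 5, headed "Patterns of subjects' disposition identifying Safety and Efficacy Analysis Population/Dataset", gives Safety Inferential and Efficacy ITT Inferential the same content, c + d. For the interim, SAP 4.5.2 begins "The populations assessed at the Interim Analysis will be the" and then names Safety Inferential as the only safety population.

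The protocol is different. For the safety population, Section 6.3.1 states "All subjects who have received at least one dose of the study medication, whether prematurely withdrawn from the study or not, will be included"; the analysis is as randomized, and 6.5 bases all safety analyses on that population. Section 6.3.3.2 says that subjects with dose adjustments or interruptions "will be excluded from the primary efficacy analysis and will not contribute to the approximately 160 evaluable subjects expected after 24 weeks"; it does not mention safety.

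**The concern.** An interruption happens after dosing starts and can be a consequence of an adverse event. The protocol allows for this. In 5.3.5.4 one of the criteria that make a laboratory abnormality a reportable adverse event is "Results in a change in study treatment (e.g., dosage modification, treatment interruption, or treatment discontinuation"; 5.3.5.5 has the same criterion for vital signs. Section 4.4.2.1 adds "Guidelines for treatment interruption or discontinuation are provided in Section" 5.2, which is the Safety Plan. The same hold can therefore turn a finding into an adverse event and remove the subject from the table meant to count it. That is selection on a consequence of the outcome.

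What is at stake is the one SAP table that compares 10 mg equivalent with placebo for safety, and the interim that is to inform internal decisions on the next steps of development. Under the literal reading, an adverse event leading to a temporary hold could not appear in that table in either arm.

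**Working it through.** **Tracing the definition**

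1. SAP 4.2.1: Safety Inferential is whichever subset serves the primary efficacy objective.
2. SAP Section 2, text under Table 3: that objective is addressed with placebo and 10 mg equivalent subjects in patterns c) or d). Details are deferred to Section 4.
3. SAP 4.2.2 and 4.5: the set is Efficacy ITT Inferential, with an exclusion for adjustment or interruption that does not depend on the reason.
4. SAP Table 4: pattern c) itself requires 24 weeks without interruption or adjustment. Pattern d) is simply enrolment in the Main Part.
5. SAP Table 5: both Inferential sets are c + d. The efficacy set has a textual exclusion that the table does not show, so the table cannot establish that the safety set lacks it.
6. No sentence in the SAP puts interrupted subjects back for safety.

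**Does Safety Global fill the gap?** It keeps the subjects but has no 10 mg equivalent column. The all-active column mixes in 4 mg equivalent subjects and the under-exposed starting doses. The tertiles use average concentration at week 12, which SAP 3.2 says takes dose interruptions into account, so an early hold can lower a subject's exposure and possibly the tertile.

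**Possible size**

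The plan has no figure to reproduce, so every rate and share here is assumed. Let r be the true adverse event rate in an arm, s the share of cases held and n the share of non-cases held. After the held subjects are removed:

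observed rate = r(1 − s) / [r(1 − s) + (1 − r)(1 − n)]

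With r = 0.20 on active and 0.10 on placebo, the true difference is 10 points and the true relative risk 2.0.

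| s active / placebo | n | Active | Placebo | Difference (points) | Relative risk |
|---|---|---|---|---|---|
| 0.10 / 0.10 | 0 | 0.18/0.98 = 18.4% | 0.09/0.99 = 9.1% | 9.3 | 2.02 |
| 0.25 / 0.25 | 0 | 0.15/0.95 = 15.8% | 0.075/0.975 = 7.7% | 8.1 | 2.05 |
| 0.50 / 0.50 | 0 | 0.10/0.90 = 11.1% | 0.05/0.95 = 5.3% | 5.8 | 2.11 |
| 0.10 / 0.10 | 0.20 | 0.18/0.82 = 22.0% | 0.09/0.81 = 11.1% | 10.8 | 1.98 |
| 0.25 / 0.25 | 0.20 | 0.15/0.79 = 19.0% | 0.075/0.795 = 9.4% | 9.6 | 2.01 |
| 0.50 / 0.50 | 0.20 | 0.10/0.74 = 13.5% | 0.05/0.77 = 6.5% | 7.0 | 2.08 |
| 0.25 / 0.10 | 0 | 15.8% | 9.1% | 6.7 | 1.74 |

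As counts with 80 per arm, s = 0.25 and n = 0, 16/80 against 8/80 becomes 12/76 against 6/78.

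For a rarer event, take a true rate of 2% and 80 dosed subjects in an arm. The chance that at least one case is visible is 1 − (1 − 0.02(1 − s))^80. This is 80% with no holds, 70% with s = 0.25 and 55% with s = 0.50.

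**The case against.** The strongest reply is that the exclusion is only inferred. SAP 4.2.1 does not state it, the text under Table 3 does not name it, and Table 5 lists only c + d. Pattern d) carries no interruption condition, so a programmer working from Table 5 alone would keep a held Main Part subject. Several passages also suggest that the exclusion was written with dose finding in mind. Protocol 4.2.1 speaks of adjustments and restarts around the interim PK and safety reviews, 4.2.4 of interruption for lack of dose confirmation, and SAP 4.2 explains the populations by the findings on the starting doses. The word interruption is nowhere defined in the visible text, most of Protocol 5.2 is redacted, and permanent discontinuation may not count as an interruption.

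This shows that the text allows two readings. It does not show that the benign one is specified: the passage under Table 3 defers to Section 4, and Section 4 contains the unqualified exclusion.

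Three limits on the harm do stand:

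- The events are not lost. They stay in Safety Global and its listings, and the IMC and SOC see unblinded data.
- The bias has no fixed direction. If non-cases are held more often than cases, the rates and the difference can be overstated, as the 10.8-point row shows.
- The relative risk barely moves unless the share held differs by arm.

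It is also fair to say that the all-dosed population of Protocol 6.3.1 survives as Safety Global. What does not survive is a 10 mg equivalent against placebo table on subjects not selected by interruption.

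**Conclusion.** The concern holds. As written, the SAP carries an efficacy exclusion into its only 10 mg equivalent against placebo safety summary, at both the interim and the final analysis, and departs from Protocol 6.3.1, 6.3.3.2 and 6.5 without giving a reason. This rests on reading SAP 4.2.1 through 4.2.2, and on interruption including holds for safety reasons, which Protocol 5.3.5.4 and 5.3.5.5 support.

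The size is unknown because the documents give no interruption rates. In the assumed scenarios the true 10-point difference reads anywhere from 5.8 to 10.8 points, and the relative risk falls materially (to 1.74) only where holds differ by arm. The point should be fixed, but it does not call the whole safety evaluation into question. Confidence is medium because the benign reading may be what was intended; even then the text has to say so.

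**What to change.** In SAP 4.2.1, define Safety Inferential without reference to the efficacy set. It would contain all subjects who took at least one dose and were randomized either to 10 mg equivalent at the Table 2 dose for their age band, or to concurrent placebo in the same age-band and randomization-stage cells. They would be analysed as randomized, with no exclusion for later interruption, adverse-event-driven dose change or withdrawal.

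The reason for a restricted set is kept: subjects with the planned IMC/SOC dose increase (Table 3: 3 to 7, 5 to 10 and 7 to 10 mg) and their concurrent placebo stay out of this comparison or go in separate columns. Use the set at the interim and final analyses, and note in Table 5 that it is not the same as the efficacy set.

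Two additions are useful but not essential: a row for adverse events leading to interruption or discontinuation, and a definition of interruption for analysis purposes.

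The cost is one or two sentences, a changed population flag and, if wanted, one table row. No new data are needed.

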#### **4.2.2         Efficacy Population**

- Efficacy ITT Global

The “Efficacy Global” population consists of all subjects who gave informed consent and received at least one dose of study medication, whether prematurely withdrawn from the study or not.

Data will be summarized according to treatment classified as derived from PK exposure: Placebo, Low Tertile, Medium Tertile, High Tertile.

- Efficacy ITT Inferential

The “Efficacy ITT Inferential” population is the primary population of interest. It consists of the subset of the “Efficacy Global” population obtained by pooling data from subjects taking balovaptan 10 mg equivalent or the concurrently randomized placebo in the corresponding age band and in the same randomization stage, as highlighted in orange in Table 3, and belonging to patterns c) or d), as highlighted in yellow in Table 4. Subjects with dose adjustments or interruptions, or on a different dose than the final dose for their age group, are excluded and do not contribute to this analysis population.

Data will be summarized according to treatment classified as: Placebo, 10mg equivalent.

The following Table shows the combination of subjects' patterns (described in Table 4) to identify the Safety and Efficacy analyses population/dataset:

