4.2.1 Recruitment Procedures

A total of approximately 340 children and adolescents with ASD will be stratified by age and sex and randomized in order to obtain evaluable data after 24 weeks of treatment from approximately 160 subjects, considering a withdrawal rate of approximately 15%–20%. *Individuals who received doses lower than intended will not be evaluable for the primary objective.*

Subjects in first adolescent/first children cohorts with dose adjustments, or who stopped and re-started treatment in the context of the interim PK and safety reviews (see Section 3.1.3), will not contribute to the approximately 160 evaluable subjects (80 subjects balovaptan 10 mg eq and 80 subjects placebo) for the primary efficacy analysis. Additional subjects will be recruited until approximately 160 evaluable subjects is reached (Section 6.3.3).

Subjects who have been discontinued for reasons of dose confirmation, prior to Week 8, will be eligible to re-screen for the OLE without having to complete the 24 weeks of double-blind treatment.

Subjects must meet all of the inclusion criteria and none of the exclusion criteria to qualify for the study. Unless otherwise stated, inclusion and exclusion criteria refer to screening.

Abbreviated re-screening (written informed consent/assent, medical history, physical examination, substance use, alcohol test, fasted laboratory safety, coagulation, serology, urinalysis, inclusion / exclusion criteria) may be allowed under circumstances in which the subject is screen-passed but could not be randomized within the 4-week screening window due to a study halt, logistical, personal, or technical reason. At no time shall the duration between the original screening visit and the abbreviated re-screening visit exceed 3 months. Abbreviated re-screening will only be permitted by the Sponsor (Medical Monitor or designee) in cases where this poses no safety risk to the subject.

Screen-failed subjects can be re-screened with Sponsor permission (Medical Monitor or designee) if there is a substantial change in the subject's general condition (e.g., prohibited medication was stopped or weight loss) and if recruitment for the study is still ongoing. Re-screening will not be allowed if the subject failed earlier to meet the disease specific inclusion criteria (e.g., SRS-2 T-score).

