**Table 4. Patterns of subjects' disposition**

| Pattern | Description: Subjects ...   | First Part
(Study part 1):
up to 8 weeks
of Treatment | Main Part
(Study part 2):
24 weeks of
Treatment |
|---------|---|--|--|
| a)      | stopped treatment prior to determination of final doses by IMC/SOC  |  |  |
| b)      | stopped treatment prior to determination of final doses by the IMC/SOC and took the opportunity to restart in the Main Part |  |  |
| c)      | allowed by the IMC/SOC to continue and complete the 24 weeks of treatment without dose interruption/adjustment              |  |  |
| d)      | enrolled in the Main Part   |  |  |

The primary **Efficacy** treatment comparison (balovaptan 10 mg equivalent dose vs. placebo) will be performed on the dataset obtained by pooling data from patients that were expected to take treatment for 24 weeks, as described by patterns c) and d) [highlighted in yellow].

**Safety** analysis will be performed separately on two datasets, according to the duration of the seamless treatment period that subjects have been exposed to. Therefore, two safety analysis datasets are identified:

- **First Part (8 weeks)** - Data from subjects that took treatment up to a maximum of 8 weeks, as described in pattern a) and 1st part of b) [framed with dotted red line]
- **Main Part (24 weeks)** - Data from subjects that took treatment up to a maximum of 24 weeks, as described in pattern c), d), and 2nd part of b) [framed with dotted blue line]

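### The primary ITT set drops individual subjects for dose interruptions that the visible text does not define, and no inferential analysis keeps them as randomized

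*SAP*

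**What the plan says.** SAP 4.2.2 builds the Efficacy ITT Inferential set, its primary population, in three steps. It takes 10 mg equivalent and concurrent placebo in the highlighted parts of Table 3, keeps disposition patterns c) and d) of Table 4, and then applies an individual filter: "Subjects with dose adjustments or interruptions, or on a different dose than the final dose for their age group, are excluded".

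Protocol 6.3.3.2 has the same filter for subjects enrolled under Version 6: "Subjects with dose adjustments or interruptions, or who were on a different dose than the final dose for their age group, will be excluded". Protocol 6.3.3.1, for earlier subjects, is narrower and does not mention interruptions: "Subjects in first adolescent/first children cohorts with dose adjustments, or who were on a different dose than the final dose". Protocol 4.2.1 ties its stop-and-restart ground to the committee reviews, naming first-cohort subjects "who stopped and re-started treatment in the context of the interim PK and safety reviews". It also has a dose ground with no cohort limit: "Individuals who received doses lower than intended will not be evaluable for the primary objective".

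SAP 4.1 describes the data for the primary comparison as "pooling data from patients that were expected to take treatment for 24 weeks", under patterns c) and d). Pattern c) covers subjects "allowed by the IMC/SOC to continue and complete the 24 weeks of treatment without dose interruption/adjustment". Pattern d), enrolment in the Main Part, has no such condition. Table 5 lists the set as c + d.

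SAP 4.5 runs inference on this set alone. SAP 3.2 keeps the exposure-tertile grouping, which is used for the Global set, descriptive. SAP 4.5.2 uses the Inferential set at the interim analysis.

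**The concern.** An interruption happens after randomization and can depend on how the subject is doing. Removing individuals for it compares subjects selected on their own course, and randomization no longer protects that comparison. Placebo matching by age band and randomization stage protects the removal of whole groups. It does not protect the removal of individuals within a group.

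Two interpretations give different primary sets. The filter may mean only stops driven by IMC/SOC dose decisions. It may also mean any pause, which is its literal wording. The documents use the word both ways. Protocol 4.2.4 uses it for lack of dose confirmation, while Protocol 5.3.5.4 and 5.3.5.5 use it for treatment changes that follow abnormal laboratory or vital-sign results. SAP 3.2 also expects interruptions during treatment.

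At stake is whether the Week 24 estimate, and the interim estimate that informs the next development step, can be interpreted as a randomized comparison.

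**Working it through.** **The passages side by side**

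- *Committee-driven stops only.* This fits SAP 4.1, which speaks of expected treatment, and pattern d), which has no interruption condition. The clause then largely repeats the removal of patterns a) and b). Such stops remain possible under Version 6, because the note to Protocol Table 2 says the dose for ages 5–7 is not confirmed.
- *Any pause.* This is the literal text of SAP 4.2.2 and Protocol 6.3.3.2. The set comes from a population that keeps subjects whether or not they withdrew early, and pattern d) does not require completion. A Main Part subject who stops for good therefore stays in. One who pauses, resumes and finishes is removed.

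**The plan's own figure (SAP 2.3)**

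Inputs: one-sided 5%, SD 12.5, difference 5 points (0.4 SD), 80 evaluable per arm.

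- n per arm = 2 × (1.645 + 0.842)² / 0.4² = 77.3, so 78.
- SE at 80 per arm = √(2/80) = 0.1581 SD.
- Power = Φ(0.4/0.1581 − 1.645) = Φ(0.885) = 81.2%.

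The stated 80 per arm and 80% power reproduce.

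**Illustration of the literal reading**

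The interruption rates and outcome gaps are assumptions; none comes from the documents. The 80 per arm is counted after exclusion, because Protocol 4.2.1 and 6.3.3.2 say excluded subjects do not count towards the 160. Let pₐ and pₚ be the interrupted shares on active and placebo, and k the deficit of interrupters against retained subjects in the same arm, in SD.

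- Bias = pₐk − pₚk.
- With no true as-randomized difference, one-sided error = 1 − Φ(1.645 − bias/0.1581).
- With a true as-randomized difference of 0.4 SD, power = Φ((0.4 + bias)/0.1581 − 1.645).

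| pₐ, pₚ, k | Bias, SD | Bias, points | Result |
|---|---|---|---|
| 15%, 5%, 0.5 | +0.050 | +0.63 | error 9.2% |
| 15%, 5%, 0.2 | +0.020 | +0.25 | error 6.4% |
| 15%, 5%, 0.8 | +0.080 | +1.00 | error 12.7% |
| 10%, 5%, 0.5 | +0.025 | +0.31 | error 6.8% |
| 5%, 15%, 0.5 | −0.050 | −0.63 | power 71.5% against 81.2% |
| 10%, 10%, 0.5 | 0 | 0 | error 5.0% |

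First row in full: 0.15 × 0.5 − 0.05 × 0.5 = 0.05 SD; 0.05 × 12.5 = 0.625 points; 1 − Φ(1.645 − 0.316) = 1 − Φ(1.329) = 9.2%.

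Unequal exclusion from a 1:1 randomization would not leave exactly 80 in each arm. With 160 kept in total, 160/(0.85 + 0.95) = 88.9 are randomized per arm and 75.6 and 84.4 remain. The SE is then 0.1584 and the error is still 9.2%.

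**Price of keeping interrupters (10% in each arm)**

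- n = 80/0.9 = 88.9 per arm; SE = √(2/88.9) = 0.150.
- They gain nothing: effect 0.9 × 0.4 = 0.36 SD, power Φ(2.400 − 1.645) = 77.5%.
- They benefit fully: power Φ(2.667 − 1.645) = 84.7%.
- Uninterrupted set at 80 per arm: 81.2%.

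**The case against.** Four counter-arguments carry weight.

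- *No flat contradiction.* A reader might infer that SAP 4.2.2 contradicts Tables 4 and 5 outright. The documents do not support that. Pattern c) already requires no interruption. Table 5 lists disposition patterns and is not a full definition, since c + d alone would also admit the 4 mg arm and subjects whose dose was raised. SAP 4.1 defines datasets and 4.2 defines populations, so 4.2.2 can be read as a further filter. The mismatch is limited to pattern d) and the expected-treatment basis of SAP 4.1.
- *A definition may exist.* Protocol 4.4.2.1 points to Section 5.2 for interruption guidelines, and Sections 5.2 and 3.1.3.1 are largely redacted. Only a statement about the visible text is safe. Neither population rule refers to those sections, though, and a definition there would not supply an as-randomized analysis.
- *The restriction looks deliberate.* The interim trigger in Protocol 6.8 and SAP 2.4 also requires no interruption or adjustment. That makes uninterrupted dosing a plausible question for the sponsor to ask. It does not justify having no analysis that retains the other subjects.
- *The study is hypothesis generating, and no arm difference in interruptions is reported.* This stands. The issue is whether the estimate can be interpreted, not a confirmatory error rate.

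A reader might also take the Version 6 rationale as promising full intention to treat. It invokes that principle only for dropping the requirement of a baseline and a post-dose assessment.

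**Conclusion.** The point holds in limited form and should be fixed. The primary set excludes individuals for an event after randomization that the visible text does not define, and it is the only set used for inference. If only committee-driven stops are meant, the clause adds little beyond removing patterns a) and b). If any pause is meant, the primary and interim estimates are biased whenever interruption rates or interrupters' outcomes differ by arm.

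Size and direction are unknown. A reader might infer that the rule favours balovaptan; nothing in the documents shows that. The illustrated range is 0.25 to 1.00 points in either direction for a 15% versus 5% split with k from 0.2 to 0.8, against a 5-point target. It is zero with equal rates and equal deficits. These figures rest on assumed rates and deficits, SD 12.5, and 80 per arm after exclusion.

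**What to change.** 1. Add to SAP 4.5 an inferential MMRM on all dosed subjects randomized to 10 mg equivalent or concurrent placebo, in the Table 3 cells eligible for the primary comparison and in patterns c) and d). Analyze them as randomized, and do not exclude anyone for an individual dose interruption. Preferably make this primary and keep the uninterrupted set as supportive.
2. If the uninterrupted set stays primary, state before unblinding whether interruption means only IMC/SOC-driven stops or any pause. Apply the rule identically in both arms, and reconcile SAP 4.2.2 and Protocol 6.3.3.2 with SAP 4.1 and pattern d).
3. Exclude dose-changed groups by factors fixed at randomization, together with their concurrent placebo: age band, stage, and randomization date relative to local IRB approval of the new dose. Age band and stage alone are not enough. Among Version 5 subjects after 1 October 2018, Table 3 shows started and increased doses side by side in one age band, depending on that approval.
4. Report exclusions by arm and reason.

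Cost: text edits and one more MMRM, with no new subjects or assessments. The statistical downside is dilution: with 10% interrupters kept, power is about 77% if they gain nothing and about 85% if they benefit fully, against 81%.
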